### **2.6.3 Cardiovascular effects**

Cardiovascular effects are not commonly reported in response to baclofen, except in studies of renal impairment or after very high doses e.g. in overdose (Nugent et al., 1986; Roberge et al., 1994). Evans et al reported a small effect of 80mg acute baclofen to increase heart rate (increase of 10 bpm) and blood pressure (121 to 125 mmHg) at 2 hours post dose, which returned to normal after 6 hours (Evans & Bisaga, 2009). In our acute study, we observed no overall significant effects on heart rate or blood pressure (Durant et al., 2018).

Methadone is reported to prolong QT interval, however there are no reports of QT prolongation following baclofen, therefore there is no indication that they are not safe to use together with respect to QT intervals.

We will monitor QT and cardiovascular parameters for signs of acute change after baclofen administration.

## **2.7 Dosing considerations- lessons learned from spasticity & alcohol dependence**

In prescribing baclofen for alcohol dependence, variability in response and the lack of robust biomarkers to guide the target maintenance dose means that the target dose for an individual is not well characterised. It is therefore titrated up until clinical benefit is achieved. Typically, 30mg daily or above is prescribed, to be taken in 3 divided doses. This minimum target dose of 30mg for this trial is supported by the literature suggesting that baclofen is efficacious in relapse prevention and in the reduction in daily drinking (G Addolorato et al., 2002; G Addolorato et al., 2007; Flannery et al., 2004)

The main dose and titration limiting factor for baclofen is sedation, though this is also variable, with some individuals able to tolerate very high doses. Consequently, high doses of baclofen were in use for some patients in alcohol dependence ( $\leq 300$ mg/d; 10x higher than initial RCT). However, since meta-analyses have since established that

doses  $\geq 60$ mg are no more effective than lower doses, safety concerns led the French authorities to approve use of baclofen in alcoholism only up to 80mg/d (Inserim et al., 2017). We have no reason to believe that doses over 90mg will be required in opiate dependence, so do not intend to go above this.

## 2.8 GABA-B receptor sensitivity

Consistent with historical prescribing of high doses of baclofen in alcohol dependence, we previously conducted a pharmacokinetic-pharmacodynamic (PK/PD) study to understand if the pharmacokinetics of baclofen and/or the sensitivity of the GABA-B system itself is altered in alcoholism that might inform what is the optimal dose (Durant et al 2018). We successfully established a protocol using a range of subjective and objective measures as well as an assay to measure plasma baclofen levels in healthy controls (n=12) and abstinent alcohol dependent individuals (n=8), who received single oral doses of baclofen or placebo in a crossover design, suggesting reduced GABA-B sensitivity in alcohol dependence. Preliminary evidence is suggestive of similarly blunted sensitivity in opiate dependence (Volpi et al., 1992). This may contribute to the variability in treatment response, variability in the emergence of side-effects, and may explain the lack of superiority of baclofen over placebo in some studies in alcoholism.

The association between the dose of baclofen, experience of sedation and other pharmacodynamic effects, and the relationship to subsequent treatment efficacy, is currently poorly understood. In addition, baclofen dose is known to be a poor predictor of blood concentrations, adding further heterogeneity to the signal. It is therefore important to develop a better understanding of this dose-response relationship. If we were to demonstrate the safety of baclofen, and proceeded with an efficacy trial using flexible dosing without knowing the PK-PD parameters, this would hamper our ability to titrate effectively. This is important because from clinical experience, individuals require resolution of their difficulties quickly so being able to titrate faster to a maximum dose, as required, will be advantageous.

We will therefore apply a similar PK-PD protocol to assess GABA-B sensitivity in opiate addicts receiving methadone with enhanced measurements to assess safety. Data derived from historical controls who took part in the previous protocol will be used in the current protocol to provide a comparator group. This will empirically test whether our opiate population are similarly more tolerant to baclofen as we found in alcoholism. If similar sub-sensitivity is observed in opiate dependence, this would be highly suggestive that it would also be found in other addictions, such as cocaine, and therefore more broadly inform development of medications targeting GABA-B system in addiction.

## 2.9 Abuse liability background/rationale

Concerns have been raised about the potential for abuse liability of baclofen (Gahr et al., 2014; Praharaj, 2018), and following reports of ‘liking’ in alcoholic populations. So far, this possibility is not borne out by evidence in RCTs of chronic baclofen in alcohol dependence. Acutely, our own study reported no significant “alcohol-like” or “drunk” effects on the subjective high assessment scale (SHAS) following 60 or 90 mg of baclofen. However on the drug expectancy questionnaire (DEQ), although there were no overall significant effects, there was a suggestion of increased “high” and “liking” effects after the 90 mg dose. Anecdotally, several participants stated that they enjoyed the effects, and likened them to those of opiates or benzodiazepines. This has potential

implications for abuse liability, particularly at higher doses, and requires further study. Another study in heavy social drinkers observed no liking effect, but did report 'good grud effect' and 'elevated mood after 80mg acute baclofen (Evans & Bisaga, 2009).

In other studies, possible evidence of abuse liability of baclofen in alcohol dependence was observed when used in combination with alcohol, but baclofen alone did not result in any measurable change in signal (Farokhnia et al., 2017).

The extent of this possible abuse liability needs to be assessed in the vulnerable opiate population due to a possible risk of misuse, in particular when combined with OST, with the aim to address this in future studies, if an abuse liability signal is detected.

## **2.10 Study Summary**

This study will evaluate the safety of acute baclofen in methadone-maintained individuals with opiate dependence. The goal of the trial is to study the safety of these drugs given in combination using an adaptive, single-blind, placebo-controlled ascending dose design investigating the impact on respiratory, cardiovascular and pharmacokinetic-pharmacodynamic (PK-PD) parameters.

This study will determine the maximum safe dose of baclofen depending on the prescribed dose of methadone. Methadone doses will vary depending on the recruited cohort, but we anticipate an average dose of ~53mg (range 5 to 120mg), based on data from local drug and alcohol services. We are seeking a minimum safe dose of 30mg baclofen in combination with a minimum of 60mg methadone. Findings will be used to inform a subsequent proof-of-concept trial of the efficacy of baclofen. We will investigate each of the four factors of i) safety, ii) dose-response, iii) potential for abuse liability and iv) objective and subjective measures of GABA-B receptor sensitivity, providing clarity on the relationship between these factors. We will include a placebo arm to evaluate the pharmacodynamic effects of baclofen, and to control for expectation effects.

Safety will be established using a Bayesian dose-escalation adaptive model which will be informed by the occurrence of dose-limiting toxicity (DLT) events at increasing doses of baclofen at the following dose levels: 10, 30, 60, 90mg. The evaluation window for all outcomes will begin at dosing and end at 5 hours post-dose, with further follow-up by phone the following day. The DLT of primary concern is respiratory depression, and we consider that the risk increases with the dose of baclofen and methadone-maintenance level. Formally, the objective is to find the combination associated with 15-25% risk of a DLT. The combination-toxicity response will be evaluated using the continual reassessment method (Wheeler et al., 2019), a model-based design for trials that aim to find the maximum tolerated dose, where the baclofen dose recommendation for each given patient with prescribed dose of methadone will be supported by the adaptive Bayesian model. Participants will be randomised (single-blind) to baclofen or placebo in a 3:1 ratio. If allocated to baclofen, participants will be dosed in groups of up to 3, with a maximum sample size of 48 allocated to baclofen, and 16 to placebo.

Outcome measures that will be used to determine the incidence of a DLT will include oxygen saturation, respiratory rate, cardiovascular measures (ECG, blood pressure) and CNS effects (sedation, alertness). End tidal CO2 and adverse events will also be monitored.

The adaptive Bayesian model will be regularly updated (after each group of up to 3 participants administered baclofen) given the observed patients' responses, providing efficiency in decision-making, by recommending the most likely safe target individualised dose. The study can therefore be stopped earlier for safety if the model suggests that 30mg of baclofen and 60mg of methadone is highly likely to be *unsafe*. The study can also stop earlier if the highest dose of baclofen (90mg) is highly likely to be *safe*, i.e. shows no DLTs with 120mg of methadone, provided that the study has also achieved sufficient data to meet secondary endpoints.

In addition to the approach described above, an evaluation of pharmacokinetic parameters will be investigated through regular blood sampling and assay of baclofen and methadone plasma concentrations. The pharmacodynamic effects of baclofen relative to placebo, and their dose separation will be determined through objective (plasma growth hormone concentrations) and subjective measures (visual analogue scales and questionnaires for drug effects, anxiety, sleep). The potential for abuse liability, relative to placebo, will be assessed using the Drug Effects Questionnaire.

GABA-B receptor sensitivity will be determined through comparison of pharmacodynamic effects in comparison with historical healthy controls, using data derived from previous work using comparable measures and time-points at the 10 and 60mg baclofen dose levels (Durant et al., 2018).

**Primary & secondary endpoints:** If we find that all dose levels of baclofen are safe up to and including 90mg in combination with 120mg methadone (primary endpoint), the study can still continue up to the maximum sample size to achieve maximum precision for secondary outcomes, explore more methadone doses (<120mg) in a variety of participants and baclofen dose-response separation, as required.

### **3. STUDY AIMS AND OBJECTIVES**

#### **3.1 Study Aims and Objectives:**

The primary objective of our programme of research is to establish whether baclofen can facilitate successful opiate detoxification. Due to the inherent risks of combining CNS depressant drugs, we will first determine the safety parameters of taking baclofen in combination with methadone in a single ascending dose study using a Bayesian dose-escalation adaptive model, incorporating pharmacokinetic-pharmacodynamic measures in a randomised, placebo-controlled design.

##### **3.1.1 Primary study objective**

1. Aim to determine whether we can safely proceed prescribing a minimum of 30mg baclofen to clients receiving a range of doses of methadone (a minimum of 60mg) through determination of:
  - Lack of CNS depressant activity using measures of respiratory function, cardiovascular function and sedation as follows:
    - Respiratory function (respiration rate, oxygen saturation, end-tidal and/or transcutaneous CO2)
    - Requirement for intervention (scored according to step-wise algorithm)

- Cardiovascular function (ECG, blood pressure, heart rate)
- Sedation (rating scales, National Early Warning Score- NEWS2, Glasgow Coma Scale)

If clinically significant CNS depressant activity is observed, this will be considered a dose-limiting toxicity (DLT) event (see section 3.4.2 for definition and criteria) and will inform the adaptive model in determining the next dose of baclofen to be administered, according to the next patient's prescribed methadone dose.

Our target dose is for 90mg baclofen to be safely prescribed in those receiving maintenance doses of methadone up to and including 120mg daily. This would provide the full range of prescribing freedom within current guidelines for prescribing of baclofen in spasticity (BNF guidelines, max 100mg/day), and meets recommendations for off-label prescribing in alcoholism (max 80mg/day granted for French temporary license (Rolland et al., 2020), and recommended efficacious doses 30-60mg/day (Agabio et al., 2018). This is also in line with prescribing of methadone as opiate substitution therapy according to Department of Health 'Orange' and NICE guidelines, both of which recommend 60mg/day of methadone as clinical therapeutic target with a maximum of 120mg/d methadone.

Our minimum acceptable dose is 30mg baclofen to be safely prescribed in those receiving maintenance doses of methadone up to and including 60mg daily. Baclofen doses below 30mg/d have not demonstrated efficacy in alcoholism (Agabio et al., 2018), and although the minimum daily recommended doses outlined in Orange and NICE guidelines is 60mg/d methadone, the majority of clients in our services are on methadone doses lower than 60mg/d (average 56.3mg/d), and our target population for those on detoxification or tapering pathways are on even lower doses (i.e. <40mg/day with methadone estimated average of 25mg). Therefore, these 'acceptable minimums' will still capture the majority of clients that we wish to enrol.

### **3.1.2 Secondary study objectives:**

Secondary aims will be investigated and findings used to inform the design of the subsequent proof-of-concept efficacy study 2 and will include:

2. Aim to identify whether there is any evidence of sub-threshold DLT respiratory, cardiovascular or sedation changes in response to baclofen relative to placebo.

Evidence of a sub-threshold DLT changes in response to baclofen would not prevent initiation of further studies in this indication, but would guide prescribing behaviour in subsequent studies.

3. Aim to determine whether there is any evidence of abuse liability signal for baclofen relative to placebo, in combination with methadone, through determination of:
  - Lack of abuse liability as measured by:
    - Drug effects questionnaire (DEQ)

Presence of an abuse liability signal would not prevent initiation of further studies in this indication, but would signal the need for additional monitoring and risk mitigation in future studies.

4. Aim to determine whether there is evidence of reduced sensitivity to baclofen relative to placebo through determination of Subjective drug response (Subjective High Assessment scale, SHAS).

Evidence of a reduced sensitivity to baclofen would not prevent initiation of further studies in this indication, but would guide prescribing behaviour in subsequent studies.

5. Explore the variability in response to baclofen at different baclofen dose levels for (i) CNS depressant activity using measures of respiratory function, cardiovascular function and sedation, (ii) abuse liability measured by DEQ and (iii) subjective drug response (SHAS)
6. Explore the variability in response to baclofen at different methadone levels for (i) CNS depressant activity using measures of respiratory function, cardiovascular function and sedation, (ii) abuse liability measured by DEQ and (iii) subjective drug response (SHAS)
7. Explore the variability in response to baclofen by gender for (i) CNS depressant activity using measures of respiratory function, cardiovascular function and sedation, and (ii) abuse liability measured by DEQ and (iii) subjective drug response (SHAS)

### ***3.1.3 Exploratory objectives***

Additional exploratory aims will be investigated and include:

8. Aim to determine whether there is evidence of reduced sensitivity to baclofen through determination of:
  - a. Objective and subjective pharmacokinetic-pharmacodynamic (PK-PD) responses using the following measures:
    - i. Plasma growth hormone levels
    - ii. Plasma baclofen levels
    - iii. Plasma methadone levels
  - b. The following measures are also to be compared with those of historic controls and those with alcohol dependence (Durant et al., 2018).
    - i. Subjective drug response (Subjective High Assessment scale, SHAS)
    - ii. Plasma growth hormone levels
    - iii. Plasma baclofen levels
9. To investigate the variability in PK-PD responses to baclofen at different baclofen dose levels
10. To investigate the variability in PK-PD responses to baclofen at different methadone levels
11. To investigate variability in response by; tolerability aspects, demographic factors (e.g. age)
12. To identify possible markers of efficacy of baclofen relative to placebo (e.g. sleep, anxiety, restless legs)

### ***3.2 Study hypotheses:***

- 1) CNS depressant activity

- a) We anticipate *no evidence of clinically significant respiratory depression* or cardiovascular changes in doses up to 90mg baclofen in those on daily methadone doses up to and including 120mg.
- b) We hypothesise that we will observe increased self-reported measures of drug effect, including sedation, with doses at or above 60mg baclofen *relative to placebo*, in combination with methadone doses at or above 60mg.
  - Increased T-SHAS drug effect score relative to placebo, at peak effect (2-3 h following dosing).
  - We hypothesise that signs of sedation in this opiate dependent cohort will be blunted in response to baclofen as compared with historic controls (Durant et al., 2018).
  - Reduced peak subjective response following baclofen administration at doses of 60mg or above.

2) Abuse liability

- a) We hypothesise that we will observe *no indication of abuse liability* of baclofen relative to placebo in combination with methadone.
  - No clinically meaningful change from placebo in DEQ 'liking' or 'want more' subscales.

3) PK-PD measures

- a) We anticipate that opiate dependent individuals will demonstrate lower sensitivity to baclofen as compared with historic controls, as follows:
  - Reduced growth hormone response relative to controls at peak effect (~2h post dose) following 60mg baclofen
  - Reduced sedation response (self-report measures) relative to controls at peak effect (2-3h post dose) following 60mg baclofen
- b) We anticipate that opiate dependent participants will demonstrate a comparable pharmacokinetic profile in response to baclofen as compared with healthy controls and those with alcohol dependence (data from (Durant et al., 2018))

4) We expect that baclofen will reduce anxiety after acute dosing and improve sleep measures during the subsequent night of sleep, compared with placebo.

### 3.4 Outcome measures

#### 3.4.1 Primary Outcome Measures

Primary outcome: The maximum safe dose of baclofen at which 15-25% of evaluable participants experience a dose limiting toxicity (DLT) for prescribed doses of methadone, where a DLT is defined in section 3.4.2 and is comprised of the following components:

- 1) Intervention level (0 to 4) as described in section 3.4.3
- 2) National Early Warning Score (NEWS2), measured at discrete time-points
- 3) Glasgow Coma Scale (GCS) score, measured at discrete time-points
- 4) QTc on ECG trace, measured at discrete time-points
- 5) Measures of respiratory function, measured continuously at discrete time-points
  - a) Oxygen saturation (SPO2)
  - b) Respiratory (ventilation) rate
  - c) Incidence of apnoea

Definitions of the evaluation window and evaluable participants can be found in sections 3.4.6 and 3.4.7 respectively, and the discrete time-points are given in section 4.3.2.

### **3.4.2 Definition of dose-limiting toxicity (DLT)**

A Bivariate Bayesian Logistic Regression Adaptive Model (see sections 4.4 and 8) will be used to determine whether safety limits are exceeded using one or more of the following outcomes as a 'dose limiting toxicity (DLT)':

- 1) Situation requiring intervention level  $\geq 4$  (section 3.4.3) at any time
- 2) NEWS2 score  $>4$  or score of 3 in any parameter (threshold for trigger of urgent ward-based response)
- 3) Measures of respiration with a persistent change in at least one of:
  - a) Reduction in  $\text{SpO}_2$  [ $\leq 91\%$  for more than 30 seconds or  $>5\%$  reduction in  $\text{SpO}_2$  for more than 30 seconds]
  - b) Reduced respiratory rate ( $\leq 8/\text{min}$ )
  - c) Absence of inspiratory airflow for  $>30\text{s}$  combined with a sustained fall in  $\text{SpO}_2$
- 4) GCS score  $<12$
- 5) Persistent QTc prolongation ( $>500\text{ms}$  or increase of  $>60\text{ms}$ ; if the initial QTc value at any time-point is prolonged, the ECG should be repeated two more times- with 5 minutes between ECG readings- and the average of the 3 QTc values used to determine DLT).

### **3.4.3 Stimulus Intervention levels:**

If marked sedation or apnoea  $>30\text{s}$  occurs, the following levels of stimulus intervention will be utilised and scored accordingly (0; no intervention).

1. Indirect noise e.g. door opening, closure, cough etc
2. Interrupt patient with direct speech
3. Touch
4. Unable to rouse patient with touch

Any intervention at level 4 or above will meet criteria for a DLT and a clinical decision will be made as to further action.

In the event of the need for clinical intervention, a crash trolley is available within the Clinical Research Facility, and a crash team is available at Hammersmith Hospital. Naloxone will be available in the ICRF as a rescue medication in the event of respiratory depression requiring intervention.

If further emergency clinical investigation and interventions are required, this will involve transfer to the emergency department at Charing Cross Hospital, via ambulance.

### **3.4.4 Secondary Outcome Measures**

#### **Components of DLT:**

- Intervention level (0 to 4) as described in section 3.4.3
- National Early Warning Score (NEWS2), measured at discrete time-points
- Glasgow Coma Scale (GCS) score, measured at discrete time-points
- QTc on ECG trace, measured at discrete time-points
- Measures of respiratory function, measured continuously at discrete time-points:
  - a) Oxygen saturation (SpO2)
  - b) Respiratory (ventilation) rate
  - c) Incidence of apnoea

#### **Respiratory measures:**

These will be investigated at each baclofen dose level, for signs of sub-threshold respiratory depression.

- SpO2- instances of <92% or of >5% reduction for more than 10 seconds
- CO2- instances of ETCO2% per breath exceeding 6.5% (Jolley et al., 2015) or a partial pressure CO2 increase by 1kPa (advice from respiratory physician)
- Respiratory rate- instances of absence of inspiratory airflow for more than 10 seconds or respiratory rate drops <9/min
- Time course of SpO2, CO2 and respiratory rate following baclofen dosing, relative to placebo.

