### **2.6.1 Respiratory depression**

Standard clinical practice for measuring respiratory depression involves monitoring for hypoventilation using pulse oximetry and respiratory rate. However, when combined with measures of carbon dioxide partial pressure (pCO2), this can provide a more sensitive and earlier indicator of respiratory depression. In addition, evidence suggests that individuals with opiate dependence may display hyposensitivity to pCO2 (Jolley et al., 2015; Tas et al., 2020).

Whilst there is no unified definition of 'respiratory depression' the most well described indicators of significant respiratory depression are as follows:

- Persistent reductions in SpO2 (e.g. <90% for more than 10 seconds; (Jolley et al., 2015)
- Absence of inspiratory airflow (apnoea) > 30 seconds combined with a sustained fall in SpO2
- Sustained ETCO2% per breath exceeding 6.5% (Jolley et al., 2015)

- Sustained CO2 partial pressure increase by 1kPa (normal range 4.7-6.0 kPa)
- Respiratory rate <9/min (from the NEWS2 score)

In the UK, NHS England has adopted the National Early Warning Score (NEWS2), first produced in 2012 and updated in December 2017, which advocates a system to standardise the assessment and response to acute illness. We will use NEWS2 definitions for the thresholds for triggering an urgent ward-based response as our criteria for determining whether a dose-limiting ‘toxicity’ (DLT) event has occurred following co-administration of baclofen and methadone. This will include monitoring of respiratory rate, oxygen saturation, body temperature, systolic blood pressure, pulse rate and level of consciousness or new confusion (ACVPU; alert, confusion, voice, pain, unresponsive).

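### The sub-threshold respiratory-rate and SpO2 counts in section 3.4.4 relax duration or persistence but not depth, so a sustained shallower fall is not counted as an instance of either

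*Combined protocol and SAP*

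**What the plan says.** Section 3.1.2, item 2, sets the objective: "Aim to identify whether there is any evidence of sub-threshold DLT respiratory, cardiovascular or sedation changes in response to baclofen relative to placebo". The same item says that such evidence would guide prescribing in later studies.

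Section 3.4.4 (Respiratory measures) says that the measures will be examined at each baclofen dose level "for signs of sub-threshold respiratory depression". For SpO2 it counts "instances of <92% or of >5% reduction for more than 10 seconds". For breathing its entry reads "Respiratory rate- instances of absence of inspiratory airflow for more than 10 seconds or respiratory rate drops <9/min". It also counts CO2 instances and lists the time course of SpO2, CO2 and respiratory rate relative to placebo.

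Section 3.4.2, item 3, defines the respiratory part of the DLT. Its stem is "Measures of respiration with a persistent change in at least one of" three limbs: (a) SpO2 of 91% or less, or a fall of more than 5%, each lasting more than 30 seconds; (b) a rate of 8/min or less, with no duration given; (c) no airflow for more than 30 seconds together with a sustained SpO2 fall. Item 2 of the same section makes a NEWS2 score of 3 in any parameter a DLT, with no persistence wording.

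Section 2.6.1 lists among its indicators of significant respiratory depression "Respiratory rate <9/min (from the NEWS2 score").

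**The concern.** An outcome meant to find change below the DLT should register events that the DLT definition does not. If its depth limit is the DLT's own, it can pick up only shorter or less persistent versions of equally deep events. A participant who stays moderately depressed for an hour adds nothing to the rate or SpO2 count.

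Section 2.10 names respiratory depression as the DLT of primary concern, and objective 2 is meant to inform prescribing in the efficacy study. The rate and SpO2 counts on baclofen could be zero while several participants had moderate, sustained change. Conversely, a non-zero rate count could consist mainly of episodes already scored as DLTs, and so say little that is new.

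**Working it through.** No sample size, power or error rate is involved. The check sets the two definitions side by side.

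| Measure | Instance (3.4.4) | DLT (3.4.2) | Depth | What separates them |
|---|---|---|---|---|
| SpO2 level | <92%, >10 s | ≤91%, >30 s | same in whole numbers | duration |
| SpO2 fall | >5%, >10 s | >5%, >30 s | identical | duration |
| Respiratory rate | <9/min, no duration | ≤8/min, persistent | same in whole numbers | persistence, undefined |
| Airflow | absent >10 s | absent >30 s plus sustained SpO2 fall | – | duration and the SpO2 condition |
| CO2 | ETCO2 >6.5% or a rise of 1 kPa | none | – | no DLT counterpart |

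**Depth.** For whole numbers, {rate < 9} = {rate ≤ 8} and {SpO2 < 92} = {SpO2 ≤ 91}. On a 0.1-unit grid the definitions differ only at 8.1–8.9/min and 91.1–91.9%.

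**The 5% limb.** The text does not say whether 5% means percentage points or a relative fall. The shallowest whole-number SpO2 that meets the depth limit, by baseline, is:

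| Baseline | Points: instance / DLT | Relative: instance / DLT |
|---|---|---|
| 92, 94, 96 | 91 / 91 | 91 / 91 |
| 97 | 91 / 91 | 92 / 92 |
| 98 | 92 / 92 | 93 / 93 |
| 99 | 93 / 93 | 94 / 94 |
| 100 | 94 / 94 | 94 / 94 |

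The instance and DLT values agree in every row, on either reading.

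**Duration.** Take an SpO2 of 91%. At 10 s it is neither an instance nor a DLT under 3a. At 11, 20 or 30 s it is an instance only. At 31 or 60 s it is both.

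**Respiratory rate.** Any persistent rate of 8/min or less is both an instance and a DLT under 3b. The non-DLT part of the count is the non-persistent readings. Because persistent is undefined for rate, that part could be anything from none (every reading of 8 or less treated as persistent) to all of them (none so treated).

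**Two examples.** A rate falling from 16 to 9/min is not below 9, so it is not a rate instance at any duration. SpO2 falling from 97% to 93% is a fall of 97 − 93 = 4 points, or 4/97 = 4.1%. It does not exceed 5% on either reading, and 93% is not below 92%, so it is not an SpO2 instance at any duration.

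**NEWS2, as a sensitivity only.** The documents do not print the NEWS2 bands. If a rate below 9/min scores 3 (an assumption suggested by section 2.6.1), any such reading at a NEWS2 time-point is a DLT without persistence. Section 4.3.2 schedules NEWS2 at five of the eight post-dose times (60, 120, 180, 240 and 300 minutes). Sub-threshold rate readings would then be possible only at 15, 30 and 90 minutes or between scheduled times. If it scores less than 3, the single-parameter rule adds nothing. The conclusion does not depend on which holds.

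**The case against.** The strongest reply is that making duration the milder dimension is a legitimate way to define a sub-threshold event, and that the plan does so. SpO2 falls of 11 to 30 seconds count. Apnoea counts from just over 10 seconds and needs no SpO2 fall. A non-persistent low rate counts. CO2 instances have no DLT counterpart, and section 2.6.1 regards CO2 as the more sensitive and earlier sign. All of this stands. A reader might infer that milder respiratory depression is never counted; the documents do not support that.

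Nor do they support the inference that SpO2 of 92–94% can never count. A fall from 100% to 94% is 6 points and meets the 5% limb.

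The reply also notes that shallower change remains visible. Section 3.4.4 lists the time course and makes NEWS2, SpO2 and rate secondary outcomes in their own right. Section 8.3.3 provides means or medians with minimum and maximum by time point and treatment group, and descriptive summaries by baclofen dose. A reading of 9/min could therefore appear as a group minimum. This answers part of the concern. But an extreme at each time point does not show whether one participant or several were affected, or whether the same participant was low throughout. Section 3.4.4 names no per-participant lowest value or largest change.

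Finally, section 8.1 makes all analyses exploratory, section 3.1.2 says that sub-threshold evidence would not prevent further studies, and section 8.3.7 leaves detail to a later SAP. These limit the severity, but the definitions still need reconciling.

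**Conclusion.** The point holds for the respiratory-rate and SpO2 instance counts, and only for those. Their depth limits equal the DLT limits in whole-number readings and differ by less than one unit if fractions are recorded. The SpO2 count still adds the 11-to-30-second episodes. The rate count is weaker, because what it adds rests on one undefined word. Neither count registers a sustained shallower fall.

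This rests on readings being recorded as whole numbers, and on the later SAP not already supplying a per-participant summary. The size of the effect on results cannot be computed, because the documents give no expected frequency of such falls. Severity is modest: the DLT definition, the dose-finding model and the stopping rules are untouched, and what is affected is how well objective 2 is answered.

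**What to change.** 1. Keep the existing instance counts, but report episodes that met the DLT separately from those that did not, by baclofen dose and for placebo.
2. Reconcile sections 3.4.2 and 3.4.4 on what persistent means for respiratory rate, so that the two definitions can be told apart.
3. Add to section 3.4.4 each participant's lowest respiratory rate, lowest SpO2 and maximum change in each from the pre-baclofen baseline, summarised by baclofen dose and for placebo. State whether these come from the scheduled readings or the continuous recordings, and use the same source in both groups. The lowest of several readings tends to be low even without a drug effect, so the placebo comparison is needed to read it.

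Moving the count bands wholly above the DLT limits would not be a good substitute: it would drop the short SpO2 episodes and non-persistent low rates that are counted now. Whether to add a further, shallower band is for the sponsor and its respiratory adviser; no cut-off is proposed here.

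The cost is some wording and a few derived variables. Section 4.3.2 already schedules rate and SpO2 at baseline and eight post-dose times, so nothing new is measured. The change to section 3.4.4 can be carried into the detailed SAP still to be agreed.
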